#### 14.1.2 Bandage Removal and Disposal

When removing bandages:

- Avoid direct contact between the treatment site and dressings.
- Wear gloves while removing dressings.
- Keep the treatment sites covered with the bandages until the time of removal.
- When it is time to remove the dressings, place the used dressings and cleaning materials in the provided biohazard container. Thoroughly spray the bandages with Lysol and securely close the container.

- Following removal of the dressing, while wearing gloves, clean the area with the subject's standard mild cleanser solution (saline, or mild soap and water).
- Avoid touching or scratching the treatment sites following removal of the bandages.
- Dress the wound as per the usual routine.

#### **14.1.3 Dry Ice Disposal**

Leave the dry ice in the container in which it was shipped and set it outside, out of reach of pets and children. Do not seal the container. Allow the dry ice to sublimate (convert to carbon dioxide gas), then dispose of the container.

#### **DO NOT:**

- Place the dry ice in the red biohazard bucket or attempt to ship it for any other reason.
- Attempt to dump dry ice in a sink, tub or toilet. The extreme cold will harm plumbing parts and pipes.
- Dispose of dry ice in garbage receptacles or garbage chutes.
- Leave dry ice in an unventilated room to evaporate. It will release a build-up of carbon dioxide into the air that can cause rapid suffocation.
- Place dry ice on a tile or laminate countertop. Instead, use a solid surface - a wood cutting board or piece of plywood is best. Dry ice is sometimes used in tile removal and may destroy the bonding agent holding the tile or laminated material in place.
- Store dry ice in a glass or air-tight container. Pressure will build up inside and could cause the container to explode.

## 15 Appendix 2 – PRO Scale

EB	epidermolysis bullosa
FDA	Food and Drug Administration
HEENT	head, ears, eyes, nose, throat
HSV	herpes simplex virus
IEM	immunoelectron microscopy
IND	Investigational New Drug application
ITT	Intent-to-treat
LTFU	long-term follow-up
MCH	mean corpuscular hemoglobin
MCHC	mean corpuscular hemoglobin concentration
MCV	mean cell volume
NC1	noncollagenous 1 domain
NC2	noncollagenous 2 domain
PP	per protocol
RBC	red blood cell count
RDW	red blood cell distribution width
SAE	serious adverse event
SD	standard deviation
WBC	white blood cell

1 Introduction

This document presents the Statistical Analysis Plan (SAP) for the protocol KB103-001, “A Phase I/II Study of KB103, a Non-Integrating, Replication-Incompetent HSV Vector Expressing the Human Collagen VII Protein, for the Treatment of Dystrophic Epidermolysis Bullosa (DEB).” The statistical plan described is prepared after an initial partial analysis was performed as the study is not a blinded study. This SAP summarizes the study design and objectives and provides details of the outcome definitions and statistical methods that will be used to completely analyze the data from Phase I through Phase II.

2 Study Objectives

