## 2 Objectives

### 2.1 Primary

- 1) To assess wound closure through post-administration imaging:
  - a. Change in surface area of a KB103-administered wound relative to the same wound at baseline and the placebo administered wound
  - b. Time to wound closure of a KB103-administered wound relative to a placebo-administered wound
  - c. Duration of wound closure of a KB103-administered wound relative to a placebo-administered wound

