### 10.5.3 Target Wound Area

Target wound surface area is obtained through on-site and at-home imaging of target areas. Change in area from baseline is evaluated for using a paired t-test for each KB103 target wound vs. control wound.

Time to closure and durability of closure will be assessed after each cycle of administrations.

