2.2 Study Objectives Phase II

2.2.1 Primary

- 8) To assess wound closure through post-administration imaging:
 - a. To assess proportion of complete wound closure of B-VEC treated wounds to that of placebo treated wounds at weeks 8, 10 and 12.
 - b. Time to wound closure of a KB103-administered wound relative to a placebo-administered wound
 - c. Duration of wound closure of a KB103-administered wound relative to a placebo-administered wound

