7.3 Treatment Compliance and Exposure

Exposure summary by treatment group will be presented for the Safety and PP populations. The distribution of subjects by the total number of weeks on therapy (baseline, 8, 10, and 12) will be presented. For the Safety population, the summary of exposure will be based on the actual treatment received.

Treatment compliance is defined as the number of wound treatment doses (KB103 and placebo) received divided by the number of doses expected, ($\times 100$) over the time period defined by the first and last treatment dose dates. Descriptive statistics for treatment compliance and the number and percentage of subjects at least 90% compliant will be presented by treatment group for the ITT, Safety, and PP populations.

8 Efficacy (Proof of Mechanism) Analyses

The study has a complete randomized-block design in which each subject serves as a block to receive all of the treatment conditions. The Phase I/II studies provided at least one pair of target wounds, with one wound being treated with placebo and one wound being treated with KB103. Efficacy measurements are taken multiple times (or repeatedly) over the on-treatment period and off-treatment period from each subject.

All data will be presented using summary statistics or frequency tables, as appropriate, and will be analyzed for superiority comparisons between KB103 and placebo treatments. The description of the sample will be done using summary statistics (n, mean, standard deviation, median, and maximum/minimum) for continuous data and using frequency statistics (counts and percentages) for categorical data. Hypothesis testing, unless otherwise indicated, will be performed at the 5% significance level (1-sided). All P-values will be rounded to four decimal places; P-values less than 0.0001 will be presented as '<0.0001' in all tables. Unless specifically stated, all confidence intervals will be two-sided with 95% coverage.

Efficacy measures collected pre-dosing will be considered as the baseline measurement (defined in [Section 6.2](#)) in this study. For all efficacy analyses, subjects will be analyzed in the group to which they were randomized.

The Sponsor, or their designee, will analyze the data using SAS® Statistical Analysis System Version 9.3 or higher.

8.1 Wound Efficacy Analyses:

8.1.1 Change in Wound Surface Area:

The efficacy analyses will be based on the observed ITT population.

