The efficacy objective is the proportion of DEB wound sites with complete wound healing from baseline ($\geq 90\%$ reduction in wound surface from baseline) in KB103 versus placebo treated intra-participant wound sites at Weeks 8, 10 and 12 as determined by the Investigator.

The number and percentage of subjects in each treatment group defined as Complete Wound Healing (CWH) will be tabulated. The null and alternative hypotheses are as follows:

Null Hypothesis $H_0: \%CWH \text{ in KB103} = \%CWH \text{ in Placebo}$

Alternate Hypothesis $H_1: \%CWH \text{ in KB103} > \%CWH \text{ in Placebo}$

Where $\%CWH$ is the percentage of wounds with a complete wound healing from baseline at week 8, 10 and 12. A one-sided significance level of 0.05 is considered

The objective of the proportion of DEB wound sites with complete wound healing from baseline ($\geq 90\%$ reduction in wound surface from baseline) will be analyzed using the Cochran-Mantel-Haenszel (CMH) test stratified by the time points (weeks 8, 10 and 12). Under the null hypothesis of no association between complete wound healing and treatment, this test statistic follows a chi-square distribution with 1 degree of freedom. The CMH test provides test of independence for the repeated evaluations at weeks 8, 10 and 12.

In addition to testing the null hypothesis, the CMH test also provides an estimate of the common odds ratio to summarize how large the treatment effect is when pooled across the different weeks of the treatment assuming the odds ratio is the same in the different weeks of treatment. This assumption will be tested using the Breslow-Day test and corresponding p-values will be provided. The null hypothesis of the CMH test is that the odds ratios within each week are equal to 1, indicating the complete wound healing proportions are the same.

A summary table with individual treatment proportions and the p-values treatment effect resulting from the chi-square test will be provided. In addition, p-values for independence of weekly evaluations (weeks 8, 10 and 12) using the Breslow-Day test will be provided.

8.1.1.1 Sensitivity and Supplemental Analyses of the Change in Wound Surface Area:

- The analysis performed in Section 8.1.1 for the efficacy objective will be repeated for the PP and LOCF imputed ITT populations.

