- The analysis performed in Section 8.1.1 for the efficacy objective will be repeated for weeks 8, 10 and 12, separately with and without stratification by time points for observed, PP and LOCF imputed ITT populations.

Other Analyses of the Change in Wound Surface Area for observed and LOCF imputed populations Include:

- The analysis performed in Section 8.1.1 for the efficacy objective will be repeated for wound healing with $\geq 50\%$ reduction in wound surface from baseline with and without stratification by time points.
- The analysis performed in Section 8.1.1 for the efficacy objective will be repeated for wound healing with $\geq 75\%$ reduction in wound surface from baseline with and without stratification by time points.

- The analysis performed in Section 8.1.1 for the efficacy objective will be repeated for wound healing with 100% reduction in wound surface with and without stratification by time points.

All the efficacy wound healing responses will be summarized by treatment and timepoints for observed and LOCF imputed ITT populations. The percent reduction in wound surface from baseline will be summarized descriptively by treatment and timepoints and treatment comparisons will be performed using the Wilcoxon rank-sum test for observed and LOCF imputed ITT populations. A subject listing will be provided for these reductions in wound surface.

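### The SAP, written after a partial analysis, departs without stated reasons from protocol v4.0: area change is demoted and tested unpaired, closure timing is defined only at ≥90%, and no IGA or PRO analysis is named

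*SAP*

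**What the plan says.** **Timing.** SAP section 1: "The statistical plan described is prepared after an initial partial analysis was performed as the study is not a blinded study". The SAP covers protocol versions 1.0 to 4.0 together (SAP section 3).

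**Area change.** Protocol 2.1 lists as primary component 1a: "Change in surface area of a KB103-administered wound relative to the same wound at baseline and the placebo administered wound". Protocol 10.5.3 gives the test: "Change in area from baseline is evaluated for using a paired t-test for each KB103 target wound vs. control wound". In its place, SAP 2.2.1 has: "To assess proportion of complete wound closure of B-VEC treated wounds to that of placebo treated wounds at weeks 8, 10 and 12". SAP 8.1.1 carries the title of change in wound surface area, but its content is a responder analysis: "The efficacy objective is the proportion of DEB wound sites with complete wound healing from baseline", where complete means at least a 90% reduction. Percent reduction appears at the end of SAP 8.1.1.1, where "treatment comparisons will be performed using the Wilcoxon rank-sum test for observed and LOCF imputed ITT populations". Yet SAP section 8 describes the design this way: "The study has a complete randomized-block design in which each subject serves as a block to receive all of the treatment conditions".

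**Closure.** SAP 8.1.1.1 repeats the responder analysis for "wound healing with 100% reduction in wound surface with and without stratification by time points", as one of the other analyses. SAP 8.1.2 defines time to closure at ≥90% reduction held for two consecutive weeks. SAP 8.1.3 ends duration of closure when the reduction falls below 90%. Neither has a 100% version. Under Protocol 5.5, a wound that closed completely in Cycle 1 ends Observation Period 1 when it re-opens.

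**IGA and PRO.** Both are secondary objectives in Protocol 2.2, with paired t-tests in 10.5.4 and 10.5.5. The SAP's Phase II objectives have no secondary tier, and SAP 8.2 lists only the IF and IEM results. IGA and PRO occur in the SAP only as rows in the schedules of its Appendix 1.

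**The concern.** A plan written after a look at part of the data should let a reader see which endpoints and tests were fixed before the look and which were chosen after it. In the available text this one does not. The Introduction explains why an early analysis was possible, but not why a primary component was replaced or a paired test became unpaired.

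Three consequences follow if the SAP is carried out as written:

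- The area comparison discards the pairing that the intrasubject design was built to provide, in a study of 11 to 14 subjects.
- Duration of closure can keep running on a wound that the protocol's own conduct rule regards as re-opened.
- For IGA and PRO the analyst has a protocol test and no SAP analysis, so it is unclear whether the tests stand.

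The one-sided 5% superiority tests in SAP section 8 can then be read only as nominal wherever they include data from the partial analysis.

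**Working it through.** Neither document gives a sample-size or power figure (Protocol 10.1 and SAP 4.1 say no formal calculation was done), so there is no figure of the plan's own to reproduce.

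**1. Endpoint count.** Of the three protocol primary components, 1a is replaced, and 1b and 1c are kept with a 90% definition only. Of the two secondary endpoints, neither has a named SAP analysis. Adding the subjects of the versions whose schedules include them (v2.2, v3.1/3.2, v4.0) gives 4 + 5 + 3 = 12 of 14 planned, or 10 of 12 on the SAP 4.1 count of up to 12. The v1.0 schedule has neither.

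**2. Wounds.** From the SAP section 3 table, 2 + 4 + 5 = 11 subjects fall under v1.0 to v3.2, and 12 have been treated to date. Two of the 11 have one KB103 and one placebo wound; nine have two KB103 and one placebo. If the wound is the unit, that is 2×1 + 9×2 = 20 KB103 wounds against 11 placebo wounds. The SAP states no unit rule, so this is one reading.

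**3. Variance.** Take equal wound variance (set to 1) and within-subject correlation r.

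- An unpaired comparison assumes 1/20 + 1/11 = 0.1409.
- The true variance of the difference in means is 0.1409 + 18r/400 − 2r/11 = 0.1409 − 0.1368r.
- The ratio of true to assumed is 0.709, 0.515 and 0.320 at r = 0.3, 0.5 and 0.7.

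**4. Simulation.** 50,000 runs per setting, same layout, normal outcomes, one-sided 5%, KB103 wounds averaged within subject for the paired tests. The correlation and the 0.7 SD effect are assumptions; the documents give neither.

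| r | Rank-sum type I error | Rank-sum power | Signed-rank power | Paired t power |
|---|---|---|---|---|
| 0 | 4.9% | 54% | 48% | 53% |
| 0.3 | 2.7% | 55% | 61% | 66% |
| 0.5 | 1.4% | 57% | 73% | 78% |
| 0.7 | 0.5% | 59% | 90% | 93% |

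A simpler layout of 12 single pairs points the same way: at r = 0.5 and an assumed 0.8 SD effect, power is 61% for rank-sum and 82% for paired t.

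**5. Closure definition.** A 90% reduction leaves up to 10% of the baseline area open. For the areas in the SAP section 3 table (up to 10, 20 and 50 cm²) that is at most 1, 2 and 5 cm². These are ceilings: a v4.0 area may include intact skin (Protocol 6.3). A wound that closes fully and then re-opens to, say, 8% of its baseline area stands at a 92% reduction. Under SAP 8.1.3 it is still closed; under Protocol 5.5 it has re-opened and Observation Period 1 is over. The documents do not say how many wounds re-open or lie between 90% and 100%.

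**The case against.** Several points on the other side have force.

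- **Threshold.** The protocol sets no numeric threshold for closure by imaging. Its phrase for 100% healed is a category of a different instrument, the IGA (Protocol 7.3), and the re-opening rule governs study conduct, not an endpoint. The SAP states its 90% rule openly and repeats the responder analysis at 50%, 75% and 100%. A reader might infer that the 90% rule contradicts a protocol definition, or that 100% must become the lead definition in SAP 8.1.1. The documents do not support either, and moving the lead threshold now would be a further change after the data look. What stands is narrower: time to and duration of closure have no 100% version.
- **IGA and PRO.** SAP section 8 promises summaries of all data, and SAP 6.1 promises listings of all eCRF data. Nothing cancels the protocol's tests. A reader might infer that these endpoints were dropped; the text shows only that no analysis is named.
- **Size of the pairing loss.** The rank-sum test is an other analysis and errs on the conservative side, so it would be wrong to infer inflated false positives. Protocol 1.6 calls wound morphology and size a major factor in healing, which makes a low correlation plausible, and below roughly 0.15 to 0.2 signed-rank has less power than rank-sum. Percent reduction is also capped at 100% and will probably tie at closure, which normal simulation ignores.
- **Scope.** The full v1.0 to v3.2 protocols are not available, and harmonising four versions may have been the motive. The SAP does not say so.

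The strongest temptation is to infer that the partial results drove the changes. Nothing in the documents shows this. The SAP discloses its timing, and the study is a pilot.

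**Conclusion.** The concern holds as a set of departures from protocol v4.0 for which the available text gives no reasons, in a plan that says it followed a partial analysis. It should be corrected, but it does not invalidate the study.

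The firmest element is the unpaired area test, which conflicts both with the protocol's paired test and with the SAP's own block design. If wounds are the unit, the true variance is 71%, 51% or 32% of the unpaired value at assumed correlations of 0.3, 0.5 or 0.7, and the nominal 5% test runs somewhere between about 3% and 0.5%. The power given up against a paired t-test at 0.7 SD is about 11, 21 or 34 percentage points (66−55, 78−57, 93−59). Near zero correlation there is nothing to gain: paired t is about equal to rank-sum, and signed-rank is slightly worse (48% against 54%).

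The duration definition can count a re-opened wound as closed, to an extent the documents do not allow one to estimate. The IGA and PRO element is mainly missing detail.

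**What to change.** 1. **Area change.** Replace the rank-sum test in SAP 8.1.1.1 with a within-subject test of area change: the protocol's paired t-test, with signed-rank as support. Report it as protocol component 1a. State the rule where two KB103 wounds share one placebo wound. Averaging the two gives one difference per subject, but it departs from the per-wound wording of Protocol 10.5.3, and the SAP should say so.
2. **Closure.** Beside the ≥90% versions in SAP 8.1.2 and 8.1.3, add 100% versions, with duration ending at the first image that shows re-opening. Keep the threshold in 8.1.1, label it plainly as ≥90%, and show the existing 100% responder analysis next to it.
3. **IGA and PRO.** Carry over the protocol's within-subject analyses for v2.2 onward, with IGA codes 5 and 6 (unable to determine, not assessed) treated as missing; or state that they are dropped, and why.
4. **Departures.** List each departure from the protocol, its reason, and whether it was decided before or after the partial analysis. State which subjects and endpoints that analysis covered, and label the affected p-values nominal.
5. **Counts.** Reconcile the 14 planned subjects implied by the SAP section 3 table with the up to 12 in SAP 4.1.

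The cost is SAP wording, some derivations and a few extra tables; no new data are needed. Closure results at 100% will be equal or less favourable, and more sensitive to measurement error near zero, which is the reason to keep the ≥90% versions alongside.

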2.1 Study Objectives Phase I

2.1.1 Primary

- 1) To evaluate safety through the incidence of adverse events (AEs) associated with KB103 post-administration.
- 2) To evaluate the expression of human collagen VII as determined by immunofluorescence (IF) and COL7A1 mRNA by RT qPCR post-administration
- 3) To evaluate the presence of anchoring fibrils as determined by immunoelectron microscopy (IEM) post-administration

2.1.2 Secondary

- 4) To assess proportion of complete wound closure of KB103 treated wounds to that of placebo treated wounds at weeks 8, 10 and 12.
- 5) To assess the duration of healing.
- 6) To access time to wound closure
- 7) To evaluate the safety of KB103 through
 - a. Change in laboratory values:
 - i. Collagen VII antibodies
 - ii. HSV antibodies
 - iii. Complete Blood Count with Differential
 - b. Changes in vital signs: blood pressure, heart rate, respiratory rate, temperature
 - c. Changes in physical exam

2.2 Study Objectives Phase II

2.2.1 Primary

- 8) To assess wound closure through post-administration imaging:
 - a. To assess proportion of complete wound closure of B-VEC treated wounds to that of placebo treated wounds at weeks 8, 10 and 12.
 - b. Time to wound closure of a KB103-administered wound relative to a placebo-administered wound
 - c. Duration of wound closure of a KB103-administered wound relative to a placebo-administered wound

2.2.2 Other

- 1) To evaluate the expression of human collagen VII as determined by immunofluorescence (IF)
- 2) To evaluate the presence of anchoring fibrils as determined by immunoelectron microscopy (IEM) post-administration

3 Overview

The Phase I/II studies were randomized placebo controlled intrasubject comparison of KB103-administered and placebo-administered wounds.

To date, KB103 has been administered to 12 patients enrolled onto 4 versions of the Phase I/II protocol. A summary of the protocols and patients enrolled are presented below.

Phase	Protocol:	SN and Date:	# of pts	Wound size	# of wounds treated	Dose	Dosing days
1	v1.0, 19Apr2018	SN0001, 4/20/2018	2, Pts 01-02 Adults	Up to 10cm ²	2: one KB103, one placebo	1e8 PFU/wound/day	0, 2, 14, 28, 30
Following v1.0, the protocol was amended to increase the frequency and PFU level of the doses, and to administer to patients age 5 and older.							
2a	v2.2, 08Oct2018	SN0008, 10/09/2018	4, Pts 03-06 2 adults, 2 children age 13&14	Up to 20 cm ²	3: two KB103, one placebo	3e8 PFU/wound/day with the option to escalate to 6e8 PFU/wound/day	1, 2, 3, 4, 5, 30, 60, 90
Following 2.2, the protocol was amended to administer KB103 every two to three days to correspond with bandage changes. The potential number of doses increased, and the dose level was set at 2e8 PFU/wound/administration.							
2b	v3.1, 12Mar2019 and v3.2*, 25Jun2019	SN0016, 3/4/2019	5, Pts 07-11 3 adults, 2 children age 14&15	Up to 20 cm ²	3: two KB103, one placebo	2e8 PFU/wound/day	Every 2 to 3 days up to 15 per month
Following 3.2, the protocol was amended to administer KB103 in 2 cycles. The age of inclusion was reduced to 2 years old. Wound areas increase to up to 50cm ² , and with the increase in area the dose was increased to 6e8 PFU per area.							
2c	v4.0, 01Aug2019	SN0024, 8/5/2019	3, TBD	Up to 50 cm ²	Up to 3; 2 KB103 and one placebo	6e8 PFU/wound/day	Every 2 to 3 days until wound closure x 2 cycles

*v3.2 clarified the long-term follow-up

4 Study Implementation

Detailed information for the protocol study visits, is provided in the sections below and in the Schedule of Events ([Appendix 1: Schedule of Events](#)).

